12.2 Statistical Analysis

All analyses will utilize the intention-to-treat (ITT) principle. All statistical tests of hypotheses will be two-sided. Baseline characteristics will be summarized by treatment arm. The primary outcome, cumulative ovulation, will be analyzed by comparing proportions utilizing a chi square test with significance set at 0.05. Dichotomous secondary outcomes will be analyzed in the same manner as the primary outcome. Two-sided t-tests will be used to compare endometrial lining thickness. Wilcoxon-Mann-Whitney tests will be used to compare number of corpora lutea. Time to pregnancy will be analyzed as a continuous variable using Kaplan-Meier survival analysis. Per-protocol analyses will be conducted to provide additional insight.

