trial of letrozole alone versus combination of letrozole and clomiphene citrate (CC) for up to 3 treatment cycles. Letrozole dosing will be increased in a stair-step fashion based on ovulation results. Participants will return for a mid-luteal ultrasound and progesterone lab to determine ovulatory status. Women will be randomized in a 1:1 ratio and the randomization scheme will be coordinated through the UIHC. Randomization will be stratified by site, age and BMI. The primary analysis will use an intent-to-treat approach to evaluate ovulatory rate in the

two treatment arms.

Objectives: To determine efficacy and safety of the combination letrozole and CC compared to letrozole alone in achieving ovulation in

infertile women with anovulation.

Primary Outcome: Ovulation will be the primary outcome determined by a mid-luteal progesterone level ≥ 3 and cumulative ovulation rate will be the primary efficacy parameter.

Secondary Outcome: Secondary efficacy parameters will include pregnancy rate (conception and clinical pregnancy), live birth rate, multiple gestation live birth rate, pregnancy loss rate (biochemical, miscarriage, ectopic) and time to pregnancy.

Side effect profile and complication rate will be monitored and reported.

Obstetric outcomes will include pregnancy complication rate, birth weight and sex, neonatal complication rate.

Ultrasound findings will be reported and compared between the two groups including: number of corpora lutea and endometrial thickness.

ClinicalTrials.gov Identifier

201906826

Population: 184 healthy women infertile women with polycystic ovary

syndrome or normogonadotropic normoestrogenic anovulation or oligo-ovulation, age \geq 18 to \leq 40. Additionally, the couple will

have no other major infertility factor.

Phase: IV

Number of Sites: 4 sites

University of Iowa Hospitals and Clinics Iowa City, IA with 2 ancillary sites

- Quad Cities Clinic, Davenport, IA
- Jordan Creek Clinic, Des Moines, IA

University of Wisconsin, Generations Clinic, Middleton, WI

Description Intervention:

of 184 women will be equally randomized to two different treatment arms at time of menses (spontaneous or induced with progestin withdrawal) or random start: A) letrozole 2.5 mg every day for 5 days (days 3-7 of cycle), or B) letrozole 2.5 mg and clomiphene citrate 50 mg every day for 5 days (days 3-7 of cycle), for a total of up to 3 treatment cycles.

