4 STUDY DESIGN

4.1 Treatment Design

This will be a multicenter, open trial of oral letrozole versus combination of oral letrozole and clomiphene citrate for the treatment of infertility in patients with oligo-ovulation or anovulation. Patients will be randomized to one of two treatment arms, to receive either an initial dose of letrozole 2.5 mg alone or clomiphene citrate 50 mg and letrozole 2.5 mg for 5 days during their menstrual cycle. Letrozole dosing will be escalated in a stair-step fashion based on ovulation results. Max dose of letrozole will not exceed 7.5 mg.

Participation in active treatment will last for up to 3 treatment cycles, approximately up to 15 weeks. Participants will be monitored at monthly intervals during expected mid-luteal phase to evaluate response to medication by evaluating ultrasound and progesterone parameters.

The dose will be adjusted according to response at mid-luteal visit.

- Anovulatory progesterone level < 3 and no evidence of follicular development and corpora lutea → increase letrozole dose on that day. This would be considered start of new treatment cycle (CD3).
- Anovulatory progesterone level < 3 with evidence of follicular development (follicle ≥14 mm) → repeat progesterone level based on LH testing (6-8 days following positive) or at 2 weeks if no positive → increase dose at menses visit (2nd progesterone is ovulatory) or increase dose at time of second progesterone if level < 3.

- Progesterone level ≥3 → maintain same dose for next treatment cycle

Anytime ovulation induction medication is started, pregnancy test to be performed prior to initiation of new treatment cycle.

Randomization will be stratified by site, age (< 35 versus \geq 35) and BMI (< 30 and \geq 30) to ensure similar comparison groups in these characteristics that highly impact outcomes. Randomization will be via a computer based central randomization to ensure adequate allocation concealment.

Enrollment will take approximately 20 months if ~ 10 subjects are enrolled per month. Active subject participation will be through completion of 3 cycles. We will follow up with patient regarding pregnancy and delivery outcomes.

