5.5 Treatment Assignment Procedures

Participants will be assigned to either combination letrozole and clomid or letrozole monotherapy in a 1:1 allocation ratio. Randomization will be blocked (with random sequences of block sizes 2, 4 and 6) and stratified by age ($< 35 \text{ versus} \ge 35$), body mass index ($< 30 \text{ and } \ge 30$), and site to ensure that balance between the treatment groups within age, BMI, and site is maintained over the enrollment period.

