5.5.1 Randomization Procedures

Participants will be randomized using randomization tables generated by a statistician and uploaded to the project in RedCap. The randomization scheme will not be accessible to study staff in order to maintain allocation concealment. Study staff will randomize subjects by entering BMI category (<30 or 30+), age category (<35 or 35+) and site on the RedCap Randomization page. Once these fields are entered and confirmed to be accurate, staff will click the "Randomize" button under treatment group to receive the participants assigned treatment."

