12.1.3 Significance Testing

Primary statistical analyses will invoke the intent-to-treat approach. Primary efficacy analysis will be performed by comparing the treatment groups with respect to the primary outcome of ovulation using Pearson chi-square test. Additional analysis will be performed using logistic regression modeling to adjust for other factors if needed such as the randomization stratification of study site, prior exposure to study medications, age and BMI. Summary descriptive statistics including mean, standard deviation, number of observations and quartiles will be provided for continuous variables; while frequencies and percentages will be provided for categorical variables. All hypothesis tests will be two-sided and all analyses will be performed using SPSS or SAS statistical software.

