12.3.2 Statistical Analyses

12.3.3 Other Secondary Analyses

Generalized estimating equations will be used as appropriate for secondary analyses of differences in means and binary outcomes where the main independent variables will be treatment group, time, and their interaction, in order to account for

within-subject variability in repeated observations over time. Potential covariates in the models include recruitment site, prior exposure to the medication, use of insulin sensitizers (metformin), baseline value of the outcome, and age.

Cox proportional hazards models and Kaplan-Meier method will be used to compare the time to pregnancy between groups.

In addition to the primary intent-to-treat analysis, a per protocol analysis will be performed as a secondary analysis.

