12.4 Missing Data

Every attempt will be made to obtain the full set of outcome values for each participant. Despite this effort, we expect there will be some missing data due to dropouts and missed visits. Missing data for binary outcomes will be calculated with both conservative (assumed negative (e.g. no ovulation) and liberal with assumed yes ovulation unless later data contradicts this. If necessary, imputation will be used.

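### The trial stratifies by site, age and BMI but tests ovulation with an unadjusted chi-square; the adjusted model is optional and open-ended, which leaves a small efficiency and pre-specification gap in a valid plan

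*Combined protocol and SAP*

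**What the plan says.** **Randomisation.** Section 5.5: "Randomization will be blocked (with random sequences of block sizes 2, 4 and 6) and stratified by age", BMI and site, with cut-points at 35 years and a BMI of 30. Section 4.1 gives the reason: "to ensure similar comparison groups in these characteristics that highly impact outcomes". The Protocol Summary counts four sites: Iowa City, its two ancillary clinics, and Wisconsin. That makes 4 x 2 x 2 = 16 strata.

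**Primary test.** Section 12.2: "The primary outcome, cumulative ovulation, will be analyzed by comparing proportions utilizing a chi square test with significance set at 0.05". Section 12.1.3 names the same Pearson chi-square. Neither section makes the primary test depend on the strata.

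**Adjusted model.** Section 12.1.3 describes logistic regression as additional, to "adjust for other factors if needed such as the randomization stratification of study site, prior exposure to study medications, age and BMI". No section says what would make adjustment necessary. The list mixes the three stratification factors with prior drug exposure, which is not one of them. Section 12.2 does not mention adjustment for the primary outcome.

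**The concern.** Balancing the arms on factors that predict the outcome makes the treatment difference less variable. An analysis that ignores those factors does not use that: its standard error is too large, so the test is conservative and some power is lost. The trial is sized for 80% power at a 20-point difference (12.1.4), which leaves little slack.

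The second issue needs no assumption about prognosis. Since neither the trigger for the adjusted model nor its covariates are fixed, both could be settled after the results of this open-label trial are known. What is at stake is how much weight that supporting analysis can carry; the primary result itself is not open to choice.

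**Working it through.** **1. The plan's own figure.** The documents give two-sided 0.05, 80% power, a 20-point difference and 10% dropout, but no control rate. Assume 60% v 80%:

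n = [1.960 x sqrt(2 x 0.70 x 0.30) + 0.842 x sqrt(0.60 x 0.40 + 0.80 x 0.20)]^2 / 0.20^2 = 81.2, so 82; 82 / 0.9 = 91.1, so 92 per arm.

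This reproduces section 12.1.4. The three treatment cycles tabulated in 12.1.1 pool to (178 + 204 + 179) / (360 + 318 + 268) = 561/946 = 59.3%. That is a per-cycle rate, so it supports 60% only loosely for an outcome counted once per woman.

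**2. Size of the chi-square.** If a fraction R of the outcome variance lies between balanced strata, its true size is about 2[1 - Φ(1.96 / sqrt(1 - R))]. Assume 25% aged 35 or over, 60% with BMI 30 or over, an odds ratio of 3 for each (both lowering ovulation), and 60% overall.

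- Stratum shares are 0.30 (neither factor), 0.55 (one) and 0.15 (both), with ovulation rates of 0.800, 0.571 and 0.307.
- Between-strata variance = 0.30 x 0.200^2 + 0.55 x 0.029^2 + 0.15 x 0.293^2 = 0.025; R = 0.025 / 0.24 = 0.105.
- Size = 2[1 - Φ(1.96 / sqrt(0.895))] = 3.8%.

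Simulation with blocks of 2, 4 and 6 in 16 strata gives 4.0 to 4.2%, because balance is imperfect in small strata. At an odds ratio of 1 it gives 5.0%.

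**3. Power in closed form, 82 per arm.** Power = Φ[(0.20 - 1.96 x sqrt(2 x W0 / 82)) / sqrt(W1 / 82)]. W0 is the outcome variance at the average of the two arms' rates, and W1 is the sum of the two arms' variances. Unadjusted, W0 = 0.210 and W1 = 0.400. Adjusted, both are averaged within strata.

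| Odds ratio (age and BMI each) | W0 | W1 | Power | Gain |
|---|---|---|---|---|
| Unadjusted | 0.210 | 0.400 | 80.4% | – |
| 1.5 | 0.207 | 0.394 | 80.9% | 0.5 |
| 2 | 0.202 | 0.384 | 81.9% | 1.5 |
| 3 | 0.192 | 0.362 | 84.0% | 3.6 |

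This charges nothing for estimating the covariate terms, so it is on the generous side.

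**4. Simulated change in power against the chi-square (points).** Site shares of 45/15/30/10% and no site effect are further assumptions.

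| Analysis | OR 1 | 1.5 | 2 | 3 | 4 |
|---|---|---|---|---|---|
| Standardised risk difference (df-corrected SE), 164 evaluable | -0.4 | 0.3 | 0.9 | 2.4 | 3.3 |
| Same, 184, missing = no ovulation | 0.0 | 0.5 | 1.0 | 1.9 | 3.4 |
| Same, 184, missing = ovulated | -0.2 | 0.4 | 0.8 | 2.6 | 3.3 |
| Leverage-corrected SE, 164 evaluable | -1.7 | -0.9 | -0.1 | 1.2 | 2.0 |
| 16-stratum CMH, 164 evaluable | -1.4 | -0.7 | -0.3 | 1.4 | 2.9 |
| Logistic Wald test, 166 evaluable (separate simulation) | 0.3 | 0.5 | 1.6 | 2.6 | – |

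The two missing-data rows follow the two rules in section 12.4. There were 10,000 trials per cell (12,000 for the Wald row), with a Monte Carlo error of 0.1 to 0.2 points on the paired differences in the first three rows. Type I error is 5.0 to 5.4% for the df-corrected version, 4.5 to 5.0% for the leverage-corrected version, and 5.2% for the Wald test.

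**5. Sensitivity.**

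- Varying the age and BMI shares, and taking a control rate of 50% or 70%: -0.1 to 1.0 points at odds ratio 1.5, 0.4 to 2.2 at 2, and 1.3 to 3.7 at 3. Adjusted type I error reached 5.8% in one sensitivity cell, where the chi-square itself was at 5.3%.
- At 75% v 95%: -0.1 / -0.1 / 0.2 / 0.5 points at odds ratios 1 / 1.5 / 2 / 3.

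**6. Site terms.** With four site terms, separation occurs in under 1% of trials at 60% v 80%, but in about 10% at 75% v 95%. It occurs in 9 to 27% if each satellite clinic recruits 4% of the women (0.04 x 184 = about 7). Using Iowa v Wisconsin removes it in those small-satellite cells, with power within 0.2 points, and cuts it to about 1 to 2% at 75% v 95%.

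**The case against.** The primary inference is already fixed: one test, two-sided, at 0.05. Choosing between two valid tests is partly preference, and the chi-square is the one that reproduces the sample size. Every driver of the gain is assumed. Section 4.1 calls the factors influential on outcomes but does not name ovulation. With the standard error that keeps type I error at or below 5%, adjustment loses power below an odds ratio of about 2, so part of the gain in the less strict version may reflect a slightly larger test. At high ovulation rates there is almost nothing to gain. All of this stands. It limits the size of the point and makes the fallback under the fix a reasonable choice.

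It does not dispose of the wording in 12.1.3. An adjusted analysis with no trigger and no closed covariate list adds little support to the primary result, and closing it costs almost nothing.

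Two stronger readings are tempting. A reader might infer that the primary result could be chosen after the data are seen. The documents do not support that, because the open choice concerns only an analysis labelled additional. A reader might also infer that the secondary GEE models overlook a stratification factor, since BMI is not listed in 12.3.3. That text reads "Potential covariates in the models include recruitment site, prior exposure to the medication, use of insulin sensitizers (metformin" and continues with other items. A list of potential covariates does not exclude BMI, and covariates may properly differ between models.

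**Conclusion.** The point holds as a minor one about efficiency and pre-specification. The chi-square is valid, and at most mildly conservative if age and BMI predict ovulation. A reader might infer that ignoring the strata invalidates the test or leaves the trial too small. Neither follows: its type I error does not rise through ignoring them, and 92 per arm is reproduced.

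At an assumed 60% v 80%, adjustment by standardised risk difference is worth about -0.4 to 0 points of power if age and BMI are not prognostic. It is worth 0.3 to 0.5 at an odds ratio of 1.5 each, 1 to 1.6 at 2, and 2 to 3 at 3. Under the stricter standard error the range is -1.7 to +2.0 over odds ratios 1 to 4, with break-even near 2. At 75% v 95% it is about 0 to 0.5. These figures rest on assumed control rates, stratum shares and prognostic effects, none of which the documents supply. The pre-specification gap rests on no such assumption.

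**What to change.** In 12.1.3 and 12.2, remove *if needed* and *such as* for the stratification factors. Commit to one main-effects logistic model with treatment, age group (<35, >=35), BMI group (<30, >=30) and site as Iowa (three clinics) v Wisconsin. Report it as a standardised risk difference with a 95% confidence interval, and name the standard error in advance. Pool site from the start, for the separation reason in step 6. Do not use a 16-stratum CMH test, which loses about 1.4 points when the strata are not prognostic.

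Preferably make this the primary analysis, with the chi-square as sensitivity. At minimum, keep the chi-square as primary and name this model as a fixed sensitivity analysis; that closes the pre-specification gap without touching the primary test.

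**Cost.** About a paragraph of text. No extra women or data are needed, because section 5.5.1 already has the values recorded: "Study staff will randomize subjects by entering BMI category (<30 or 30+), age category (<35 or 35+) and site". If the model is made primary, type I error is about 5.0 to 5.4% (5.8% in one sensitivity cell). Up to 0.4 points of power are lost if the strata are not prognostic, or 1.7 with the stricter standard error.

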12.3 Secondary Analyses

12.3.1 Descriptive Summary

We propose a number of secondary analyses, including assessing differences in conception and clinical pregnancy rates, live birth rates and multiple pregnancy rates, pregnancy loss rates (biochemical, miscarriage, ectopic), time to pregnancy, ultrasound measures (number of corpora lutea, endometrial thickness and pattern by ultrasound) and obstetric outcomes of pregnancy complication rate, birth weight, and neonatal complication rate. We will also evaluate side effect profile of both groups and compare % percentage of patients that would not take study treatment due to side effects.

12.3.2 Statistical Analyses

12.3.3 Other Secondary Analyses

Generalized estimating equations will be used as appropriate for secondary analyses of differences in means and binary outcomes where the main independent variables will be treatment group, time, and their interaction, in order to account for

within-subject variability in repeated observations over time. Potential covariates in the models include recruitment site, prior exposure to the medication, use of insulin sensitizers (metformin), baseline value of the outcome, and age.

Cox proportional hazards models and Kaplan-Meier method will be used to compare the time to pregnancy between groups.

In addition to the primary intent-to-treat analysis, a per protocol analysis will be performed as a secondary analysis.

12.3.4 Sub study Analyses

In our sub study analyses we will compare the differences in corpora luteal number and endometrial thickness between the two arms of the study. Previously reported ultrasound parameters for Letrozole are presented in the table below.

Mean and standard deviation ultrasound parameter assumptions for letrozole treatment group

treatment group					
Endometrial	6.2 ± 2.2 in	Mejia et al, 2018	34 cycles of		
Thickness (mm)	Letrozole group		letrozole 2.5 and		
			33 cycles of		
	8.3 ± 3.6 in Combo		combo (letrozole		
	group		2.5 + CC 50) in		
			women with		
			PCOS on cycle		
			day 12-14		
Number of follicles >	0.4 ± 0.56 in	Mejia et al, 2018	34 cycles of		
10 mm	Letrozole group		letrozole 2.5 and		
			33 cycles of		
	2.0 ± 2.13 in Combo		combo (letrozole		
	group		2.5 + CC 50) in		
			women with		
			PCOS on cycle		
			day 12-14		
Largest follicle size	11.71 ± 4.50 in	Mejia et al, 2018	34 cycles of		
(mm)	Letrozole group		letrozole 2.5 and		
			33 cycles of		
	15.61 ± 5.9 in		combo (letrozole		
	Combo group		2.5 + CC 50) in		
			women with		
			PCOS on cycle		
			day 12-14		

An additional sub study analysis will report subsequent fertility treatments and outcomes in patients who do not have an ongoing pregnancy at the conclusion of participation. The follow up window for these participants will be 10 months.

12.3.5 Sample size calculation

Considering midluteal endometrial thickness previously reported in ovulatory letrozole treatment cycles and hypothesized ovulation rates, the planned sample of 184 patients will have 94% power to detect a .25mm difference in midluteal endometrial thickness between the two arms among patients who ovulate. Assuming follicles >15mm on CD 12-14 in our preliminary study are indicative of corpora lutea, the planned sample will have 90% power to detect a 0.3 difference in mean number of corpora lutea among patients who ovulate.

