Unlike CC, letrozole has a peripheral action whereby it blocks aromatase and the cytochrome P450 enzyme complex. This results in a peripheral hypo-estrogenic state, leading to increased FSH secretion. Letrozole also increases serum LH, androstenedione and testosterone levels (12). The rise in androgen levels increases follicular sensitivity to FSH by synergistic action with insulin-like growth factor (13-15) and FSH gene amplification (15, 16). The subsequent rise in serum estradiol provides a negative feedback on FSH, limiting multi-follicular recruitment and allowing endometrial proliferation (12).

[figure not shown]
CC has an antiestrogenic effect on endometrial development, which has not been demonstrated with letrozole. It is important to evaluate and confirm that by combining these two medications we do not see thinning of the endometrium demonstrated by ultrasound.

Herein we propose that the combination of letrozole and CC has an additive effect whereby CC decreases pituitary sensitivity to estrogen negative feedback while letrozole directly decreases serum estradiol, further promoting FSH secretion. We speculate that these alternate actions increase rates of ovulation and pregnancy in women with PCOS.

Preliminary Data

Addition of CC to letrozole improves ovulation rate: We investigated the impact of combining CC with letrozole as compared to letrozole monotherapy in 70 women with PCOS. We found that the combination of letrozole 2.5 mg and CC 50 mg nearly doubled the ovulation rate as compared to use of letrozole monotherapy (77% vs. 43%, P=0.007; rate ratio for ovulation (95% CI) 1.80 (1.18 to 2.75) (17). These results were achieved in a single treatment cycle, without any multiple gestations in our study cohort. In concordance with our findings, a prospective observational trial of combination letrozole and CC in patients who had previously failed CC and letrozole monotherapies found evidence of improved

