ovulation, with development of a dominant follicle in 82.9% of cycles (18). While it is possible that the difference between the two arms in our preliminary study could be explained by a dosing effect, the ovulation rate in our combination treatment group was higher than the 61.7% cumulative ovulation rate across five cycles of letrozole monotherapy with increasing doses up to 7.5 mg (4). Our finding of a similar ovulatory rate within the letrozole monotherapy arm to that previously reported suggests an additive effect of the combination of these medications.

0.286

Addition of CC to letrozole does not negatively impact ultrasound parameters: Data from our pilot study suggest among the subgroup who ovulated, endometrial thickness and number of follicles were similar across treatment arms (Table 1). This is reassuring in that CC is not having a negative impact on

the endometrium and multi follicular development appears limited.

Both a commentary (19), and Fertility and Sterility Live Global Journal Club praised our pilot study, but emphasized the need for additional

•	•	Letrozole + CC Group n=25	p value
# of follicles > 15 mm	0.5 (0-1)	1 (0-1.5)	0.081
Largest follicle size (mm)	15.5 (10.0-18.3)	17.0 (13.5-19.5)	0.228

 8.6 ± 3.9

 7.4 ± 2.3

Table 1. Ultrasound characteristics among patients who ovulated

studies to evaluate escalating dosages, multiple cycles, live birth, and multiple gestation with this novel combination treatment. Given our promising initial data, the goal is to expand on our pilot and conduct a trial with escalating doses of letrozole across three cycles of either letrozole monotherapy or combination therapy in 184 women. This will provide not only additional data on ovulation rates but provide essential information on side effects, multiple gestation rate and live birth rate which will better situate us completing a multicenter study evaluating live birth rate.

Endometrial lining (mm)

Significance and Innovation

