3.2 Secondary Research Hypothesis and outcome measures

We will analyze secondary outcomes however due to sample size will not be able to power differences in pregnancy rate and live birth rate. Descriptive secondary outcomes will include positive pregnancy test, clinical pregnancy, and ongoing pregnancy. We will also evaluate number of corpora lutea determined by ultrasound, endometrial thickness and pattern by ultrasound. We will also monitor adverse events during treatment and side effect profile of both treatment arms.

We will evaluate pregnancy outcomes and report any fetal anomalies.

- 1. The combination treatment will result in higher live birth rate
 - a. Outcome measurement: live birth rate

- 2. The shortest time to pregnancy will be with the combination treatment.
 - a. Outcome measurement: time to pregnancy
- 3. Treatment with the combination will have a similar singleton pregnancy rate compared to treatment with letrozole.
 - a. Outcome measurement: Singleton pregnancy and singleton pregnancy rate; singleton pregnancy is defined as presence of single intrauterine gestational sac with a single fetal pole and observable heart motion. Multiple pregnancy rate will also be compared.
- 4. Treatment with the combination will have a similar pregnancy loss rate compared to treatment with letrozole.
 - Outcome measurements: Pregnancy loss (defined as spontaneous abortion occurring before 13 weeks gestation), biochemical (positive hCG test with spontaneously dropping hCG levels), ectopic pregnancy or pregnancy of unknown location
- 5. Side effect profile will be similar between both treatment groups.
 - a. Outcome measurements: # of days of reported side effects and acceptability of side effects.
- 6. Endometrial thickness and corpora lutea number will be similar between the two groups.
 - a. Outcome measurement: Endometrial thickness and corpora luteal number on CD21-23 transvaginal ultrasound or approximately 6-8 days following detection of LH surge. These outcomes will also be evaluated based on dosing.

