12.1.4 Sample Size Calculations

Considering the cumulative ovulation rate over 3 cycles from PPCOS II, data from our initial pilot study, and a clinically relevant increase in ovulation, we designed the study with 80% power to detect a 20% absolute difference in ovulation rate among women treated with letrozole combined with CC, compared to those treated with letrozole monotherapy. Allowing 10% dropout following randomization requires 92 patients per arm, or 184 total. Allowing for an additional 15-20% screening failure rate requires 220 consented to reach our randomization goal.

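### The 94% power claimed in section 12.3.5 for a 0.25 mm endometrial-thickness difference is about 6-10% with the SDs the plan prints

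*Combined protocol and SAP*

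**What the plan says.** Section 12.3.5 claims "94% power to detect a .25mm difference in midluteal endometrial thickness between the two arms among patients who ovulate". It describes its basis as "Considering midluteal endometrial thickness previously reported in ovulatory letrozole treatment cycles and hypothesized ovulation rates", but prints no SD, no source and no number of ovulating women. The same section claims 90% power for a difference of 0.3 in mean corpora lutea, "Assuming follicles >15mm on CD 12-14 in our preliminary study are indicative of corpora lutea".

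The document prints endometrial SDs in two places:

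- **Section 12.3.4** tabulates assumptions from the pilot trial at cycle day 12-14, with an SD of 2.2 mm on letrozole and "8.3 ± 3.6 in Combo".
- **Table 1 in section 2.1** covers pilot patients who ovulated and shows 8.6 ± 3.9 and 7.4 ± 2.3 mm. The accompanying text says "among the subgroup who ovulated, endometrial thickness and number of follicles were similar across treatment arms".

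Section 12.2 specifies a two-sided t-test for endometrial thickness.

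**The concern.** A difference of 0.25 mm is about one ninth of the smallest printed SD (0.25/2.2 = 0.11) and one sixteenth of the largest (0.25/3.9 = 0.06). Standardized differences that small normally need thousands of patients, and this comparison is restricted to the ovulating part of 184.

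The endpoint matters to the plan. Section 2.1 says it is important to confirm that, on the combination, "we do not see thinning of the endometrium demonstrated by ultrasound". Hypothesis 6 in section 3.2 is that "Endometrial thickness and corpora lutea number will be similar between the two groups". If readers believe the trial has 94% power at 0.25 mm, they will take a non-significant t-test as near-proof that the arms are alike. If the real resolution is well over 1 mm, the same result would leave a sizeable thinning unexcluded.

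**Working it through.** **Inputs**

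- Difference 0.25 mm (12.3.5); two-sided t-test (12.2); alpha 0.05 (stated in 12.2 for the primary outcome, assumed here).
- 92 women per arm (12.1.4).
- SDs of 2.2 and 3.6 mm (12.3.4), and 2.3 and 3.9 mm (Table 1). Table 1 is broken in the text available, so the last pair was run with both arm assignments.
- Ovulating women per arm are not stated. Three scenarios were used:
  - 55 v 74: 0.60 × 92 = 55.2 and 0.80 × 92 = 73.6. This takes roughly the 61.7% letrozole rate cited from PPCOS II, plus the "20% absolute difference in ovulation rate among women treated with letrozole combined with CC".
  - 40 v 71: the pilot rates, 0.43 × 92 = 39.6 and 0.77 × 92 = 70.8.
  - 92 v 92: every woman ovulates.
- A deliberately generous fourth case counts three ovulatory cycles from every woman as independent: 3 × 92 = 276 per arm.

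**Method**

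SE = √(SD₁²/n₁ + SD₂²/n₂), noncentrality = 0.25/SE, and power from the noncentral t distribution (pooled degrees of freedom for equal SDs, Welch otherwise).

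**Can the 94% be recovered?**

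Not directly, because the inputs are not printed. Solving for the SD that would give it at 55 v 74: √(1/55 + 1/74) = 0.178, the required noncentrality is about 3.54, and SD = 0.25/(3.54 × 0.178) ≈ 0.40 mm. The corresponding values are 0.36 mm at 40 v 71, 0.48 mm at 92 v 92 and 0.83 mm at 276 v 276.

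**Power at 0.25 mm with the printed SDs**

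Worked case, SD 2.2 mm in both arms at 55 v 74: SE = 2.2 × 0.178 = 0.392, noncentrality = 0.25/0.392 = 0.64, critical t = 1.979 on 127 df, power 9.7%.

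| SD letrozole / combination (mm) | 40 v 71 | 55 v 74 | 92 v 92 | 276 v 276 |
|---|---|---|---|---|
| 2.2 / 2.2 | 8.8% | 9.7% | 12.0% | 26.6% |
| 2.2 / 3.6 | 7.3% | 7.7% | 8.7% | 16.6% |
| 2.3 / 3.9 | 7.1% | 7.4% | 8.2% | 15.0% |
| 3.9 / 2.3 | 6.5% | 7.0% | 8.2% | 15.0% |
| 3.9 / 3.9 | 6.2% | 6.5% | 7.2% | 11.7% |

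**Women per arm needed for 94% at 0.25 mm**

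n = (1.960 + 1.555)² × (SD₁² + SD₂²)/0.25². This gives about 1,913 (2.2 / 2.2), 3,518 (2.2 / 3.6), 4,052 (2.3 / 3.9) and 6,013 (3.9 / 3.9).

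**What the planned sample can resolve, at 55 v 74**

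| SD letrozole / combination (mm) | Detectable, 80% power | Detectable, 94% power | 95% CI half-width |
|---|---|---|---|
| 2.2 / 2.2 | 1.11 mm | 1.39 mm | 0.78 mm |
| 2.2 / 3.6 | 1.45 mm | 1.82 mm | 1.02 mm |
| 2.3 / 3.9 | 1.55 mm | 1.95 mm | 1.09 mm |
| 3.9 / 2.3 | 1.67 mm | 2.10 mm | 1.17 mm |
| 3.9 / 3.9 | 1.96 mm | 2.46 mm | 1.37 mm |

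Across the three ovulator scenarios, the 80% detectable difference runs from 0.91 mm (92 v 92, SD 2.2) to 2.18 mm (40 v 71, SD 3.9).

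**Corpora lutea**

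No SD is printed for follicles above 15 mm (12.3.4 gives SDs only for those above 10 mm), so the 90% cannot be reproduced. Table 1 does give medians and interquartile ranges for the count: 0.5 (0-1) and 1 (0-1.5). A crude normal conversion, IQR/1.35, gives SDs of 0.74 and 1.11. Power at 0.3 is then about 45% at 55 v 74, and 39-57% from 40 v 71 to 92 v 92. That is rough for a skewed count, but it puts the 90% in doubt too.

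**The case against.** The strongest reply is that section 12.3.5 says it used midluteal values from ovulatory letrozole cycles, whereas the SDs in 12.3.4 are from cycle day 12-14 and include cycles without ovulation. On this view the check uses inputs the section never claimed, and shows only that the 94% cannot be reproduced. It is true that the sponsor's input is unknown. But the reply saves the figure only if the midluteal SD between women is about 0.4 mm. The pilot women who did ovulate had SDs of 2.3 and 3.9 mm, and nothing in the document suggests a value near 0.4.

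A second reply is that 0.25 is a slip. At 55 v 74 with SD 3.9 mm in both arms, a difference of 2.5 mm (0.25 cm) gives 94.7% power. Another route also lands close: the standard error 2.2/√34 = 0.38 mm, used as if it were the SD, gives 94.4% at 51 v 68. Because two different slips fit, the document cannot say which occurred, if either. The printed sentence is wrong on the printed inputs in both cases.

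Third, section 12.3.3 allows generalized estimating equations with the baseline value as a covariate, so 27% is not a strict ceiling. With SD 2.2 mm, even the 276 v 276 case would need a residual SD of 0.83 mm, hence a baseline correlation of √(1 − (0.83/2.2)²) ≈ 0.93. At 55 v 74 it would have to be about 0.98.

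Finally, nothing in the plan says that similarity will be inferred from p > 0.05. That is fair, but sections 3.2 and 12.2 set no margin and name only the t-test, so the power statement is all a reader has for judging a null result.

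**Conclusion.** The concern holds. On every endometrial SD the document prints, power at 0.25 mm is about 6-10% in the two main ovulator scenarios and at most 12% if every woman ovulates, against the stated 94%. The size depends on the assumed number of ovulating women and on the printed SDs being a fair guide to midluteal variability. The conclusion does not, because the SD would have to fall to about 0.36-0.48 mm to reverse it.

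This is a secondary, sub-study statement. It does not affect the 184 or the primary comparison of ovulation. It is still worth correcting, because it overstates what the trial can show about endometrial thinning.

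**What to change.** 1. In 12.3.5, correct the difference or the power from the sponsor's own calculation, and print the SD, its source and the assumed ovulators per arm. Check the units of the 0.25 figure.
2. If the printed SDs are the basis, state the difference detectable with 80% power as about 1.5-1.7 mm (1.1-2.0 mm for SDs of 2.2-3.9 mm), and say that this assumes 55 v 74 ovulating women.
3. Recheck the 90% corpora lutea power, and print the SD for follicles above 15 mm and the ovulator numbers used.
4. In 12.2, add that hypothesis 6 will be reported as a between-arm difference with a 95% confidence interval, and that similarity will not be concluded from a non-significant test.

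The cost is one or two sentences in 12.3.5 and one in 12.2, together with a less favourable statement of sensitivity. The sample size, primary analysis and visits stay as they are.
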